After completion of the 1-month data collection, participants will receive items donated by the Alcohol Drug and Mental Health (ADAMH) of Franklin County system that includes a resource directory, grocery bag that includes an ink pen, stress ball, bag clip, and hand sanitizer. Additionally, The Ohio State University James Cancer Center has donated a scarf, insulated cup, and lip gloss.

After completion of the study, at 6 months, the participant will have the option of either receiving a \$75.00 Amazon gift card or retain their self-care monitoring equipment (Home BP monitor and weight scale). If the participant selects the Amazon card, then we will provide them with a postage paid package to return the self-care equipment.

IRB Protocol Number: 2020B0182
IRB Approval date: 06-28-2020
Version: 11-13-2020
2-23-2024
5-26-2024
10-01-2021

After completion of the COVID ALL OF US COPE survey at 6 months, you will receive a \$10.00 Amazon gift card.

Participants will also waist tape measurer, pill box, and kick stand for their smartphone.

The reason for any participant's discontinuation and the date of withdrawal will be recorded in the participant's case file. The participant's case file, which will be completed up to the point of withdrawal, will be retained for five years. The study report will include reasons for participants' withdrawals as well as details relevant to the withdrawal. Each participant will be encouraged to complete the full course of the intervention assignment and study assessments. However, it is made clear to participants that they may discontinue study participation at any time for any reason. The reason for early withdrawal must be documented in the participant's case file and in the participant tracking document.

Handling of withdrawal. If a participant is withdrawn from participation in the study at any time at his or her request, or at the IRB or Principal Investigator's discretion, the reason(s) for discontinuation shall be documented thoroughly in the source documents and participant's case file. All participants who are withdrawn prematurely will undergo the procedures outlined in the discharge visit.

Procedures overview. Using an IRB approved script, we will recruit, screen and enroll participants until we have 32 qualified participants. An initial visit will be scheduled to obtain baseline survey data (approximately 90 minutes), and complete the baseline cognitive function testing (60 minutes). Per participant's preference, the survey data and cognitive function testing may be done on two separate days.

Procedures.

Informed consent. Interested participants will be given access to the self-initiating process to provide information (email and phone) and to contact a member of the study team with questions, prior to consent. This will also serve as pre-screening to review inclusion/exclusion criteria for the eligibility of the participants. The eligible participants will be consented using a REDCap-based electronic consent form. The consent form has been developed in REDCap, a secure, web-based, HIPAA-compliant, data collection platform with a user management system allowing project owners to grant and control varying levels of access to data collection instruments or data (e.g. read only, de-identified-only data views). Self-initiating process can be done on personal portable electronic devices using posted QR codes or web-links on study fliers, social media, or websites.

The steps to consenting are as follows:

1. Potential participants would access the Verbal Script for Obtaining Informed Consent The Ohio State University Consent to Participate in Research via REDCap link provided on the study recruitment materials.
2. The consent link will have a prescreen feature.
 - a. If a person says no to one of the inclusion criteria (black/African American, female, diagnosis of hypertension, age 45-65) questions, they would be thanked and told that they do not qualify.

IRB Protocol Number: 2020B0182
IRB Approval date: 06-28-2020
Version: 11-13-2020
2-23-2024
5-26-2024
10-01-2021

- b. This would also be yes for any of the exclusion criteria (no access to computer with internet or Smartphone, diagnosis of resistant hypertension defined as blood pressure that remains above goal despite concurrent use of three antihypertensive agents of different classes, one of which should be a diuretic/water pill).
 - c. If the person meets the eligibility criteria, then the verbal script for obtaining informed consent will appear.
 3. At the end of the consent form, the person would click a checkbox to be enrolled in the study.
- If the person says no, then they will be thanked for their time.
4. If the person checks yes, another box would open to request their contact information (phone, email, mailing address) and query as to whether or not they want documentation linking them to the research.
 5. We will contact the participant to confirm eligibility for the study, answer any questions they may have about the consent form, verify verbal consent (logged in REDCap), and schedule the first study visit. We will mail a copy of the consent form to the participant for their records.

Baseline survey data will be collected as listed in Table 1. Data will be collected using a private room via phone or Zoom secure video conference. The participant can enter by invitation only. If the participant does not have access to a touch screen tablet or computer, they may be able to borrow one of our two iPads from the College of Nursing. This would be mailed to the participant with return postage paid.

1. Meetings will require a password by default. These passwords will be embedded in the meeting URL (link) by default.
2. Annotations will not be available to participants by default.
3. The ability to join a meeting before the host or alternate host joins will be disabled by default.
4. Participants will not be able to change their names by default.
5. The questions to surveys will be read to the participant and answers recorded on survey forms and entered into REDCap under the participant's study ID number. Response cards will be given to participants to follow along with the interviewer.

In the future, we may have similar research studies. The consent form will also include the opportunity for participants to partner with us for potential future studies that are related to hypertension and health in Black and African Americans. The scope of the request for the participant's contact information will be access to the following by the study team/PI:

The contact information will not be provided to other investigators for similar research projects without further informed consent (e.g., recruitment registry).

- a. First and last name.
- b. Address
- c. Phone number (cell/home)

IRB Protocol Number: 2020B0182
IRB Approval date: 06-28-2020
Version: 11-13-2020
2-23-2024
5-26-2024
10-01-2021

d. Email

The consent form will also provide an opportunity to participate in future research. We will obtain the participant's permission to contact them in the future (yes/no). They are not required or obligated to provide their contact information for future research opportunities.

The contact information of participants, who agree to be contacted in the future, will be stored in the secure R:drive at the College of Nursing.

Intervention Protocol. The eCo-Chin and group sessions will be recorded, using a hand held recorder, to monitor fidelity and to retrain the RN, LD, and AC group leader as needed. Before each eCo-CHIN session, the RA will conduct a check-in to measure BP and review the sleep and physical activity logs (see below). At the end of each session, the participants will identify one goal that is specific, measurable, acceptable, relevant, and time-bound (SMART). They will also receive, via U.S. mail, the Daily Food and Physical Activity Diary and the National Sleep Foundation Sleep Diary to complete as homework. The diaries will be collected weekly as a measure of treatment enactment.

Interactive PowerPoint presentations of educational content will be delivered via Zoom.

Participant protection and Zoom. Using the **Only authenticated** users can join setting will prevent guests who do not have an Ohio State Zoom account from entering the session. Since the meeting includes non-university participants, the PI will use the following strategies to control who can attend.

- Participants only with access can join
- Turn off the option to Join before Host
- Turn on the Waiting Room
- Meeting will be password protected

Participants will be informed that the Zoom group sessions will be recorded using a hand held recorder. Additionally, we will obtain the participant's permission in advance. Participants will be encouraged to use their camera to facilitate interaction. However, participants will be given the choice to turn off their camera and microphone and use the Zoom Chat if they prefer. Participants may use an avatar image of themselves in the Zoom room. Each cohort will choose a pseudonym for their cohort. Participants may share their contact information, not required, if they would like to support one another in their health goals. The study staff will not provide participants with each other's' contact information. The four weekly group classes will be audio recorded using a hand held recorder. The recorded sessions will be converted and stored electronically in a secure system called REDCap. The audio recording of the group classes will be then destroyed.

Presented at the National Minority Quality Forum April 2020, the Coronavirus Anxiety Workbook (<https://thewellnesssociety.org/free-coronavirus-anxiety-workbook/>) uses evidence based stress reduction techniques to promote mental well-being during a pandemic. The following topics are listed in the workbook: Planning Your Information Diet; My Spheres of Influence Worksheet; Practical Wisdom for Tolerating Uncertainty; Reducing Anxiety With Thought Challenging; Reducing Anxiety Through Distraction Activities; Starting a Planning Practice; Starting a Daily Gratitude Practice; Starting a Daily Breathing Practice; Improving the Quality of Your Social Connections; Developing a Regular Exercise Routine; and Creating Your Stress-Resilience

IRB Protocol Number: 2020B0182
IRB Approval date: 06-28-2020
Version: 11-13-2020
2-23-2024
5-26-2024
10-01-2021

Action Plan. Each session will begin with a 15-30 minute check in on what went well, challenges, and Coronavirus Anxiety workbook. The Coronavirus Anxiety Workbook topics are complementary and the sessions will tie together the themes of comprehensive stress and emotional management through blood pressure knowledge/self-monitoring, diet, interpersonal communication skills building, and sleep hygiene.

Session 1 (LD Dietitian Interventionist). "DASHing Through Life provide an overview of the DASH eating plan and why it is important for African Americans. The goal is to help these women to make daily life changes. The content was developed by a Registered Dietitian Nutritionist using evidence based materials from Academy of Nutritional dietetics and the American Heart Association. Critical Thinking Strategies were used to engage participants to think about barriers and solutions to the incorporation of the Coronavirus Anxiety Workbook skills to reduce emotional eating. Part of the Critical Thinking Strategies is goal setting and review. We will review modifications to healthy eating of traditional "soul food/southern" meals. At the end of the session, participants can use Critical Thinking Strategies to have their food diary reviewed by the dietitian and the group. For homework, participants will complete Coronavirus Anxiety Workbook on Developing a Regular Exercise Routine; and Creating Your Stress-Resilience Action Plan.

Session 2 (RN Interventionist). The session will begin with a review of foods that promote stress reduction followed by monitoring Your Blood Pressure covers diagnosis, causes, risk factors, symptoms, interventions, and how to self-monitor BP. This includes an interactive didactic lecture and slide presentation and distribution of personal arm-automatic BP monitors. Research assistants will work with participants to demonstrate use of the home BP monitor. The participants will watch a video and practice measuring their BP. Reviewing stress related factors that may increase blood pressure. Building resilience and managing emotions in stressful times. Participants will receive the Coronavirus Anxiety Workbook-A tool to help build resilience during difficult times. For homework, participants will identify strategies to reduce information overload and complete the Spheres of Influence worksheet.

Session 3 (RN Interventionist). The session will begin with a review of blood pressure monitoring followed by stress and emotion regulation management through interpersonal communication skills training. We cover effective communication (verbal and nonverbal), thinking, listening, and speaking. Participants learn about communication and the effects of stressful communication on the body's physiological responses. They are encouraged to talk about their positive and negative experiences communicating with family and friends in the context of the Black culture. Participants learn problem solving skills to address communication breakdown and practice what they have learned. For homework, review Improving the Quality of Your Social Connections from the Coronavirus Anxiety workbook; Practical Wisdom for Tolerating Uncertainty; and Reducing Anxiety With Thought Challenging. Participants will also complete a sleep diary.

Session 4. (RN Interventionist). Sleep lifestyle. The session will begin with emotion regulation review followed by the RN review of barriers and facilitators to good sleep, sleep management practices, and relaxation before bedtime. This will include a review of foods that help with sleep. Participants practice a 10-minute mindfulness body scan. Identification of preferred physical activities is introduced by the RN as a tool to improve sleep. Throughout the session, the RN reinforces collaboration with their health providers to seek treatment for sleep problems. The

IRB Protocol Number: 2020B0182
IRB Approval date: 06-28-2020
Version: 11-13-2020
2-23-2024
5-26-2024
10-01-2021

group will review the sleep diaries that they completed the previous week and share strategies. For homework, participants will review Reducing Anxiety Through Distraction Activities and Starting a Planning Practice and Starting a Daily Gratitude Practice from the Coronavirus Anxiety workbook. They will be contacted by study staff via phone to review their final homework assignment.

The sessions will be recorded using Zoom so that those who miss a session can access and listen to the lesson.

Using an investigator-generated form, trained research staff will provide a self-care coaching call to participants (approximately 10-20 minutes) to review questions and provide ongoing support of self-care. The calls will be made twice a month for four months. The data will be entered into the REDCap Coaching call form.

Field Notes

Research staff may describe their thoughts about factors they observed that contributed to the quality of each encounter by writing a brief field note. The field notes will be documented in REDCap. A descriptive qualitative analysis will be conducted to categorize themes.

Incidental findings. Blood pressure. The following guidelines will be used to triage unanticipated blood pressure findings; if average systolic BP is >150 or diastolic BP is >110, we will instruct the participant to follow up with health provider or an urgent care center if the participant does not have a health provider.

Data Validity/Integrity

It is the responsibility of the Principal Investigator to ensure that all team members handle data and related documentation appropriately. All participant information, including source documents must be reviewed by the PI and clinical team and entered into the REDCap database. There will be ongoing processing of data and quality checks by the study statistician and or PI.

Recruitment:

Participant recruitment will be tracked and reviewed in the weekly meetings of the research team. In order to maintain confidentiality, the list, which includes the names of all potential participants, will be kept separately from the documentation and tracking spreadsheet in the College of Nursing R: Drive (duo authentication). Tracking will be carried out to determine which and how many individuals are interested in study participation, are eligible for study participation, enroll in the study, and complete the first assessments. Enrolled participants will be given code numbers and their study participation will continue to be tracked via spreadsheet in the College or Nursing R:Drive using and Excel spreadsheet. This will include documenting the occurrence and date of completion of data collection at each time point and their participation in the intervention.

Quality Assurance:

IRB Protocol Number: 2020B0182
IRB Approval date: 06-28-2020
Version: 11-13-2020
2-23-2024
5-26-2024
10-01-2021

To minimize data-entry error and data-management miscoding, data will be entered into REDCap directly and we will have a paper forms as a back-up. If the data has to be transcribed into REDCap from a paper form, we will do a double data entry process. PI [name] and or designated study staff will review the data collected and all related documentations weekly.

Data Storage:

Consent forms will be stored in REDCap. Participant lists (ID number and demographic information) will be stored in the College of Nursing R:Drive on a spread sheet. The PI and designated study staff will have access to data. All participant data collected via REDCap will be labeled only with a code number. These coded data will be kept separate from the master list that links participants to their consent forms. Only the PI and designated research study staff will have access to the data.

This study will utilize REDCap (Research Electronic Data Capture), a software toolset and workflow methodology for electronic collection and management of clinical and research data, to collect and store data. The OSU Center for Clinical and Translational Science (CCTS) Research Informatics Services will be used as a central location for data processing and management. REDCap provides a secure, web-based application that provides an intuitive data manipulation interface, custom reporting capabilities, audit trail functionality, real-time data monitoring/querying of participant records, and variations of data exporting/importing. REDCap is hosted by OSUWMC IT in the Ackerman Datacenter ([name])

REDCap instance is located on internal OSUWMC network. Remote access to this network can be obtained over an encrypted VPN tunnel (AnyConnect) This VPN uses Protocol: DTLS and Cipher: RSA_AES_128_SHA1. Background checks are performed on all staff that are on the network or obtaining VPN access.

Termination for Significant Risk:

Although the study is deemed low risk and adverse events are not anticipated, diligent monitoring will occur as specified above under Adverse Events Protocols. A participant that expresses concern about his or her participation or reports distress associated with receiving the eCo-CHIN intervention may be asked to discontinue participation in the study if there is concern about participant safety and wellbeing or about the safety and wellbeing of others. Likewise, if one of the research assistants, interventionists or supervising members of the Research Team expresses a concern about a participant's safety or wellbeing, the Office of Responsible Research Practices Adverse Events Reporting process will be used and it is possible that the participant could be asked to discontinue participation if there were concern about his or her, or others, safety and wellbeing.

D. Internal Validity

The quasi-experimental design is a limitation but it is an acceptable design for a feasibility study. We will repeat measures of stress and emotion regulation over three time points (baseline, 1 month, 6 months) to reduce regression to the mean as an internal validity threat.

E. Data Analysis

IRB Protocol Number: 2020B0182
 IRB Approval date: 06-28-2020
 Version: 11-13-2020
 2-23-2024
 5-26-2024
 10-01-2021

We will use descriptive statistics to examine variable distribution, check for outliers and summarize sample characteristics and outcome measures at each time point. For Aim 1, we will use descriptive statistics to quantify the rates of recruitment, attendance, and attrition for feasibility. Using a semi-structured list of open-ended questions, we will elicit participant feedback regarding the acceptability of the intervention. The Consensual Qualitative Research Method (CQR) ⁶⁹ will be used to analyze qualitative data. The responses to open-ended questions will be transcribed. The transcripts will be reviewed by three members of the research team to determine core domains (themes).

“The preliminary lists will be presented to one another, providing examples from the transcripts. After deliberation, a list of the domains will be agreed upon. Each team member will then review the data and verify the quality of the consensually chosen domains, and subsequently meet again to discuss and arrive at a consensus on a final list of domains. Categories will be labeled based on the frequency of occurrence of themes in the data (Nguyen et al., 2013, pp. 3-5)”

For Aim 2, we will first use descriptive statistics and trend plots to examine the outcomes (stress and emotional regulation) over time (baseline, 1-month, and 6-months). Next, Paired T-tests will be performed to examine the change of each outcome at 1-month (vs. baseline) and at 6-months (vs. baseline). Sample size from this pilot study will not have sufficient power to detect small-to-medium effect sizes for within-group difference (e.g., 54% power to detect a Cohen’s d of 0.5 with a two-sided significance level of 0.05). Therefore, we will not rely on statistical significance. Instead, we will estimate point estimates, 95% confidence intervals and effect sizes. These estimates along with clinical significance will guide our results interpretation and inform the sample size determination for a future NIH funding mechanism. For Aim 3, changes in RBANDS measure will be analyzed using the same approach for Aim 2 (baseline and 6 months). For Aim 4, Co-I [name], Health Economist, will use descriptive statistics, trends, and plots to evaluate allocations of resources and estimate costs of the intervention at various stages.

F. Project Timeline

The development of this group-delivered intervention will be an iterative process, and we will use this pilot data to submit an external grant for a 12-week intervention through the National Institutes on Aging in 12-18 months.

Table 2. Project timeline.

Activity	1-2 months	3-4 months		5-6 months	7-8 months	9-10 months	11-12 months
IRB application	X						
Recruitment		X		X			
Data collection (baseline, 1-month, 6-months)		X		X	X	X	
Delivery of Intervention		X		X	X		
Preliminary data analysis of baseline data for an NIH grant in February 2022				X	X	X	X
Final data analysis						X	X
Dissemination							X

IRB Protocol Number: 2020B0182
IRB Approval date: 06-28-2020
Version: 11-13-2020
2-23-2024
5-26-2024
10-01-2021

References

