- Cultural tailoring by use of culturally familiar terms in the educational materials, connecting mindful awareness to spirituality, and delivery of sessions in a familiar setting (home).
- The use RBANS via a web-based platform to explore the use of eCo-CHIN to enhance cognitive function (processing speed, attention, and executive function).

III. Procedures/Approach

Introduction. The theoretical framework for our intervention is adapted from the Information-Motivation-Behavioral Skills model.^{49,50} The intervention has three components that include knowledge of basic information regarding an illness/disease (hypertension), motivation through learning in a socially supportive environment (eCo-CHIN), and behavioral skills acquired to manage a chronic illness through improving self-efficacy (confidence in managing hypertension) to cope with stress and support emotional regulation. Demographic, clinical, and lifestyle factors and neurocognitive factors are proposed to influence the adoption of eCo-CHIN, stress management and emotion regulation strategies. Cognitive function is an exploratory feasibility aim to administer testing via teleconference.

A. Research Design

Quasi-experiment pre/post design to test the eCo-CHIN intervention in Black women with hypertension.

The intervention consists of four web-based weekly group sessions, lasting 90 minutes each that are delivered by a Registered Nurse (RN) and a Licensed Dietitian (LD).

B. Sample

Thirty-two Black women age 45-65 (middle-age as defined by the U.S. Census) will be enrolled in 3 cohorts (6-8 participants), with one new cohort beginning every 4-6 weeks. Inclusion criteria are English speaking, self-identification as Black/African American, diagnosis of hypertension (treated with medications and or lifestyle management), female sex, and access to a smart phone or a computer capable of connecting to the Internet (80% of Blacks have a smartphone).⁵¹ Exclusion criteria are no access to computer with internet or Smartphone or diagnosis of resistant hypertension defined as blood pressure that remains above goal despite concurrent use of three antihypertensive agents of different classes, one of which should be a diuretic/water pill.

Measurement/Instrumentation

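### Two follow-up visits cannot reduce regression to the mean when there is only one pre-programme measurement and no comparison group

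*Combined protocol and SAP*

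**What the plan says.** Section III.A describes a "Quasi-experiment pre/post design to test the eCo-CHIN intervention in Black women with hypertension", and no comparison group appears anywhere. Under I. Objectives and in Table 1, the stress and emotion-regulation scales are scheduled at baseline, 1 month and 6 months. The procedures overview has one initial visit for the baseline surveys. Its option of two days separates the surveys from cognitive testing and repeats no scale.

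Section III.D first concedes: "The quasi-experimental design is a limitation but it is an acceptable design for a feasibility study". The next sentence says these measures will be repeated "over three time points (baseline, 1 month, 6 months) to reduce regression to the mean as an internal validity threat".

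For Aim 2, section III.E says "we will first use descriptive statistics and trend plots to examine the outcomes (stress and emotional regulation) over time" and then: "Paired T-tests will be performed to examine the change of each outcome at 1-month (vs. baseline) and at 6-months (vs. baseline"). It adds "Therefore, we will not rely on statistical significance", and on point estimates, 95% confidence intervals and effect sizes it says: "These estimates along with clinical significance will guide our results interpretation and inform the sample size determination for a future NIH funding mechanism".

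**The concern.** Regression to the mean arises in a pre/post study when the baseline is temporarily high among those who enter and later scores drift back without any effect of treatment. A second measurement before treatment, or a comparison group, can separate that drift from an effect. Measurements after treatment has begun cannot, because each is still compared with the same baseline.

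Aim 2 sets out to determine initial efficacy. A reader who accepts the sentence in III.D would think one rival explanation for a fall in stress had been partly dealt with, and would discount a limitation that still stands in full. The planned confidence intervals express imprecision and do not cover this bias.

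**Working it through.** The plan gives no figure for regression to the mean, so there is none to reproduce. The 54% power in III.E concerns precision and does not enter this check.

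**Inputs from the protocol**
- Pre-programme measurements of these scales: one (Objectives, Table 1, procedures overview).
- Contrasts: 1 month minus baseline, and 6 months minus baseline (III.E).
- Selection on the outcome: none by rule. Section III.B reads "Inclusion criteria are English speaking, self-identification as Black/African American, diagnosis of hypertension" and continues with female sex and internet access; no stress or emotion score is required. Self-referral is allowed (Recruitment), which makes selection on a passing state possible but does not show it.
- Stability of the scales: not given. Table 1 lists Cronbach alpha of 0.71 to 0.94 for the stress and emotion scales. Alpha describes consistency between items, not correlation over months. No reference mean is given.

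**Model (assumed).** Scores have population mean 0 and SD 1; there is no programme effect and no time trend. Let *e* be the amount by which entrants' mean baseline is raised through selection on the baseline score, and *r* the correlation between baseline and a follow-up visit. The expected follow-up mean is *r* × *e*, so

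expected change = *r* × *e* − *e* = −(1 − *r*) × *e*.

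The number of follow-up visits does not appear in this expression. Higher scores on the perceived stress and emotion-regulation scales are worse, so a negative value looks like improvement.

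| Elevation *e* (SD) | *r* = 0.8 | *r* = 0.7 | *r* = 0.6 |
|---|---|---|---|
| 0 | 0 | 0 | 0 |
| 0.25 | −0.05 | −0.075 | −0.10 |
| 0.5 | −0.10 | −0.15 | −0.20 |
| 0.8 | −0.16 | −0.24 | −0.32 |

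The last row corresponds to every entrant being above the mean, an extreme case that the entry rules do not impose. Stably high stress does not regress and adds nothing to *e*.

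**The two contrasts together.** A simulation with no true effect (4 million draws) agrees with the formula:
- No selection: 0.00 in both contrasts.
- *e* = 0.80, *r* = 0.7 at both visits: −0.24 and −0.24 SD; 1-to-6-month change 0.00.
- *e* = 0.80, *r* = 0.8 at 1 month and 0.6 at 6 months: −0.16 and −0.32 SD; 1-to-6-month change −0.16.
- *e* = 0.17, *r* = 0.7 at both visits: −0.05 and −0.05 SD.
- *e* = 0.17, *r* = 0.8 then 0.6: −0.03 and −0.07 SD.

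Both contrasts are exposed, and not necessarily equally.

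**What an extra pre-programme measurement would do.** With *e* = 0.80 and *r* = 0.7 between all occasions, using a second pre-programme score as the baseline brings the bias from −0.24 to 0.00, and averaging the two pre-programme scores brings it to −0.12. The protection comes from measurements before the programme.

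**Trend plots.** A fall by 1 month that then holds fits both regression to the mean and a lasting effect. If correlation with baseline weakens over time, a further fall by 6 months can also be artefact, as in the −0.16 and −0.32 case.

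**The case against.** The strongest objection concerns the order of enrolment. The consent steps put prescreening, electronic consent and a confirming contact before the first visit is scheduled, so self-selection precedes the baseline measurement. If entrants are selected on an earlier state with elevation *s*, the expected change is −(*r*₀ − *r*₁) × *s*, where *r*₀ and *r*₁ are the correlations of that earlier state with baseline and with follow-up. Equal correlations give zero. Decay leaves some bias: with *s* = 0.5, *r*₀ = 0.8 and *r*₁ = 0.6, it is −(0.8 − 0.6) × 0.5 = −0.10 SD. This stands as a reason to think the larger values in the table unlikely. The perceived stress scale also asks about the past month, which dampens momentary highs, although the daily stress inventory covers only 24 hours. Neither point makes the follow-up visits protective.

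Second, III.D says reduce, not remove, and three points show more than two. No fall at 1 month, or a full return to baseline by 6 months, would argue against simple regression to the mean. That is fair, but it is weak help with interpretation and not control of bias.

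Third, the plan is already modest: the design limitation is conceded, feasibility and acceptability are primary, establishing efficacy is described as a long-term goal, and significance is not relied on. All of this stands and limits the severity. It does not make the sentence correct.

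**Conclusion.** The concern holds as a minor error of rationale. Section III.D claims a protection that one pre-programme measurement, no comparator and two contrasts against the same baseline cannot give. This conclusion follows from the design and needs no assumed number.

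The size of any bias in this study cannot be estimated from the documents, and it may be zero. Every elevation and correlation used above is assumed, and the tabulated values hold only if selection acts on the score at the baseline moment. They show that both contrasts are exposed; they do not size the bias here. No planned estimate is computed wrongly. What changes is how Aim 2 may be read: as uncontrolled change from baseline.

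**What to change.** Replace the second sentence of III.D with:

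> Repeated follow-up does not control regression to the mean or time trend, because there is one pre-intervention measurement and no comparison group; Aim 2 changes are uncontrolled changes from baseline and will be interpreted as such.

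The present text makes no claim about time trend. Those words are included because the same design feature leaves it uncontrolled, and they can be dropped without affecting the correction.

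As advice only, III.E could add that the uncontrolled pre/post effect size will not by itself set the between-arm target of a later randomised trial, and that the pilot mainly supplies the SD, the pre-post correlation, and recruitment and attrition rates.

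The cost is one replaced sentence, plus one optional sentence, and a more modest Aim 2 claim. No data, visits or analyses are added.
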